10. MONITORING

10.1 Data Safety Monitoring Plan

Monitoring of the study will be conducted by a qualified clinical trial monitor according to an established monitoring plan. All subjects who are diagnosed with OSA will also be overseen by a certified sleep provider throughout the duration of the study, who will then continue to follow them once study activities have ceased. Subjects who are not already established patients in the U-M MS/sleep clinic will be referred for expedited sleep clinic follow up following their PSG diagnosis of OSA. Whenever possible, these clinical visits will occur in tandem with study visits.

Although none of the measures in this study assess self-harm, in the event that a participant mentions suicidal ideation or other severe mental distress that could result in harm to self or others, [name] (Co-Investigator), who is a licensed psychologist, will contact the participant by phone and complete a standard self-harm/suicide assessment, taking appropriate action (e.g. referral for mental health services, contacting emergency services) as needed. All safety related incidents will be reported to the PI and the IRB according to relevant protocols.

10.2 Monitoring Plan and Information

To assure adequate protection of the rights of human subjects, per 21 CFR 312.50 and 312.53, the study will be monitored to ensure that the study is implemented in accordance with the protocol and applicable federal and local regulations, that proper informed consent procedures were followed and to insure the integrity and quality of the data.

A qualified trial monitor will be selected, per 21 CFR 312.53(d) to monitor the trial in accordance with the protocol and all applicable regulatory requirements. A monitoring plan will be established to ensure the quality and integrity of the data through pre-investigation, periodic site visits, review of adverse events/subject records, etc. The Michigan Institute for Clinical and Health Research (MICHHR) will assist with the selection and support of the monitor assigned for this proposed clinical investigation and prepare the monitoring plan.

11. DATA HANDLING AND RECORD KEEPING

11.1 CRFs / Electronic Data Record

CRFs, in paper or electronic format, will be utilized and maintained by the study staff. Entries made in the CRF must be verifiable against source documents, unless the CRF is considered to be the source document.

11.2 Record Retention

Per 21 CFR §312.62, study records will be retained for a minimum of 7 years after the investigation is discontinued.

12. ETHICS

12.1 IRB

Prior to study commencement, the study will be reviewed and approved by the Institutional Review Board (IRBMED, University of Michigan, Ann Arbor, MI).

12.2 Subject Information and Consent

A study team member will explain to each subject the nature of the study, its purpose, the procedures involved, the expected duration, the potential risks and benefits involved and any discomfort it may entail. Each subject will be informed that participation in the study is voluntary and that he/she may withdraw from the study at any time and that withdrawal of consent will not affect his/her subsequent medical treatment or relationship with the treating physician.

This informed consent will be given by means of a standard written statement, written in non-technical language. The subject should read and consider the statement before signing and dating it, and should be given a copy of the signed document. No patient can enter the study before his/her informed consent has been obtained.

The informed consent form is considered to be part of the protocol, and will be submitted for IRB approval.

13. STUDY DISCONTINUATION CRITERIA

Stopping Rules for Safety Reasons

Subjects who demonstrate evidence of severe excessive daytime sleepiness (as evidenced by ESS scores ≥ 16 at baseline) will result in exclusion from study. Subjects with extreme OSA that is accompanied by signs of cardiopulmonary compromise or severe nocturnal hypoxia on baseline PSG will also result in study exclusion unless they are randomized to expedited PAP arm. In such cases, subjects will be referred for expedited sleep clinic follow-up.

Discontinuation of a Subject

In the event a patient drops out of the study or is discontinued due to protocol violations, all attempts will be made to exit the patient in accordance with the protocol requirements.

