For Aim 2, subjects who meet criteria for OSA on baseline PSG or recent U-M Sleep Lab in-lab clinical PSG (n~140) will be randomized into one of 2 groups: expedited positive airway pressure (PAP) therapy, followed by repeat cognitive testing at 3 months post-PAP (Group 1, n~93), or standard care PAP therapy which will commence following completion of month 3 testing (Group 2, n~47). Mean changes from baseline in cognitive test scores will be compared between groups.

Assessments

The aims of this study are to assess the relationship between sleep apnea severity and cognitive dysfunction in MS patients with OSA (Aim 1), and to examine the effects of positive airway pressure (PAP) on cognitive function in MS patients with OSA (Aim 2).

N~175 patients who screen positive for high OSA risk on a validated screening questionnaire (STOP-Bang), or who already carry a diagnosis of OSA but are not yet using PAP on a compliant basis will be invited to participate.

Consenting subjects with STOP-Bang scores positive for ≥ 2 risk factors for sleep apnea who are at high risk for OSA but who do not yet have a University of Michigan Sleep Laboratory PSG will undergo baseline (month 0) in-lab PSG and baseline neuropsychological (cognitive) testing. Subjects who have a recent diagnosis of OSA based on recent (within 1 year) in-lab clinical University of Michigan Sleep Laboratory PSG who have not yet started using PAP treatment compliantly will undergo baseline cognitive testing and their in-lab clinical PSG data will be used for baseline analyses. Subjects who have a diagnosis of OSA based on non-UM in-lab PSG or PSG > 1 year prior to screening will undergo new baseline PSG and baseline cognitive testing.

Subjects who meet criteria for OSA on baseline or clinical PSG (n~140, anticipated) will then be randomized into one of 2 groups (2:1 randomization): immediate treatment with PAP (Group 1, n~93) followed by repeat neuropsychological testing at 3 months post-PAP; or standard of care application of PAP at 3 months, after completion of repeat neuropsychological testing (Group 2, n~47). Analyses will focus on relationships between standard PSG measures (including the Respiratory Disturbance Index, oxygen desaturation index, and minimum oxygen saturation), innovative new quantitative PSG measures and cognitive test scores, as well as mean changes from baseline in individual and composite cognitive test scores following treatment with PAP therapy.

Statistical Methods

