4.2 Exclusion Criteria

- 1) Physical, psychiatric or cognitive impairment that prevents informed consent, PSG, PAP use, or reliable longitudinal follow-up
- 2) Cardiopulmonary conditions that may increase sleep apnea risk
- 3) Current treatment, such as PAP, for obstructive or central sleep apnea
- 4) History of surgical treatment for OSA
- 5) Nervous system diseases other than MS that may predispose subjects to OSA (such as Parkinson's disease, amyotrophic lateral sclerosis, or recent stroke)
- 6) History of concomitant central nervous system disease that could influence cognition, such as large vessel territory stroke, Alzheimer's disease, Parkinson's disease, or Lewy body dementia
- 7) Concomitant systemic autoimmune disease with secondary central nervous system involvement (including CNS lupus or neurosarcoidosis).
- 8) Pregnancy
- 9) Evidence of clinical MS relapse within the last 30 days prior to enrollment
- 10) Systemic high dose steroid use (1 gram IV methylprednisolone daily for 3-5 days or equivalent) for an MS relapse within the last 30 days prior to enrollment
- 11) Unwillingness to initiate PAP therapy if clinically indicated
- 12) Severe depression at screening per the Patient Health Questionnaire-8 (PHQ-8)
(The PHQ-8 is a brief, self-administered questionnaire that evaluates core symptoms associated with major depressive disorder. Scores range from 0 to 24 based on the frequency and severity of depressive symptoms over the previous two weeks.)
- 13) Anticipated initiation, dosage change, or discontinuation in medications that could, per the opinion of the investigators, influence cognitive test scores from baseline to follow-up, including MS disease modifying therapies, hypnotic agents, narcotic-based medications, benzodiazepines, antispasmodics, or 4-aminopyridine
- 14) ESS scores ≥ 16 on baseline visit
- 15) Subjects with extreme OSA accompanied by signs of cardiopulmonary compromise (RDI > 60 respiratory events per hour with severe nocturnal hypoxia or unstable ECG rhythms on PSG), will be excluded unless they are randomized to immediate PAP arm
- 16) Any other condition or treatment that in the opinion of the investigator could affect subject safety or study eligibility

Table 1: STOP-Bang questionnaire	
Snoring	Do you snore loudly (louder than talking or loud enough to be heard through closed doors)?
Tired	Do you often feel tired, fatigued, or sleepy during the daytime?

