5. STUDY TREATMENTS

5.1 Allocation to Treatment (see also 6.4)

Randomization Process: Subjects who meet all Inclusion/Exclusion criteria, including OSA on baseline or clinical PSG, will be randomized (2:1 randomization) to expedited PAP therapy (Group 1, n~93), or standard care PAP therapy (Group 2, n~47), after the subject has signed consent, completed the baseline activities, Randomization will be stratified by sleep apnea severity (RDI < or >=30) to minimize imbalances in apnea severity between groups.

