5.2 Blinding

PSG technicians, PSG interpreters, and study staff who conduct and score neuropsychological tests will remain blinded to group allocation for the duration of the study. **The subject, PI, co-investigators, coordinators, and statistician will not be blinded.**

5.3 Treatment with Positive Airway Pressure (PAP) Therapy: Unless already performed at U-M sleep lab within the past year, all subjects who are diagnosed with OSA on baseline or clinical PSG (n~140) will undergo PAP titrations* and be prescribed clinical PAP therapy by clinicians involved in the study or the subject's treating sleep provider. PAP therapy is considered standard clinical care for patients with obstructive sleep apnea. PAP is a mode of respiratory ventilation that blows air into the nose (or nose and mouth) to splint the upper airway open during sleep. PAP therapy can be delivered at a continuous pressure (CPAP), at different levels during inspiration and expiration (BiPAP), or at a range of auto-adjustable levels depending on the patient's breathing (AutoPAP)*. In order to determine which pressure setting most effectively treats an individual's sleep apnea, an overnight PAP titration study is typically required. This study is similar to a PSG in terms of overnight monitoring but also involves fitting of various masks which are then hooked up to the subject and PAP machine to test the effectiveness of various PAP settings, and to determine which mask/setting is most tolerable for the subject. PAP titration studies will be scored by certified PSG technologists and interpreted by a board-certified sleep physician, who will then place an order for PAP equipment at appropriate settings with a local durable medical equipment (DME) provider. DME will be covered by the subject's insurance.

* In some cases, insurance carriers will not cover the cost of an in-laboratory PAP titration, and instead will recommend an “auto-adjusting” PAP machine (also known as AutoPAP, or APAP) so that patients diagnosed with OSA may begin PAP without requiring a PAP titration.

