6.7 Month 3 Visit with repeat Cognitive Testing

Group 1: 3 months after PAP initiation

Group 2: 3 months after randomization

All randomized subjects will undergo the following assessments:

- 1) Focused medical and surgical history as it relates to MS, sleep, and cardiopulmonary history
- 2) Medication review
- 3) PAP compliance review for Group 1
- 4) Fatigue, insomnia, and sleepiness assessments (see 7.2)

- 5) Pain, anxiety, and quality of life assessments (see 7.2)
- 6) AE/SAE review
- 7) Repeat neuropsychological testing (see 6.2)
- 8) PAP titration for group 2 (if applicable)*

* Group 2 subjects are encouraged to undergo PAP titration on the night of the Month 3 visit. If they agree to this approach, the PAP titration will be scheduled around the time of the Month 2 visit.

6.8 Post-Study Follow-up phone assessment for Group 2 (1 month after Month 3 visit)

Following the Month 3 visit (and once the PAP titration is complete) , for Group 2 subjects who still express a desire to proceed with PAP treatment, the study team will contact the subject and/or DME company (phone or email) to confirm that a PAP prescription has been faxed to the subject's designated DME company), and if applicable, that UM sleep clinic follow up has been made. Three phone contacts will be attempted. Any barriers to the PAP prescription process will be passed on to sleep clinic staff for appropriate action. If no clinic follow up has been scheduled per the subject's account (and the subject still desires a sleep clinic appointment), the study team will contact appropriate UM sleep clinic personnel to contact the subject.

SCHEDULE OF ACTIVITIES

Study Activity	Baseline Visit	Baseline PSG visit	Month 0	Month 1	Month 2	Month 3
Demographics	X					
Medical/Surgical History	X			X	X	X
Medication review	X			X	X	X
Height, weight, neck circumference	X					
EDSS self-report	X					
AE/SAE review	X			X	X	X
Baseline neuropsych testing (all subjects)	X					
Repeat neuropsychological testing (OSA subjects)						X
Baseline PSG (all subjects who do not have U-M PSG within the past year)		X				
Randomization (for subjects with OSA on baseline PSG)			X			
PAP titration/prescription for Group 1			X			
PAP compliance review for Group 1				X	X	X
Fatigue (FSS), insomnia (ISI), and sleepiness (ESS) surveys	X			X	X	X
PROMIS/NeuroQOL measures	X					X

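### Section 13 allows randomised subjects to be exited for undefined protocol violations, nothing keeps them in the Month 3 comparison, and Group 1 never-starters have no Month 3 date

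*Combined protocol and SAP*

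**What the plan says.** Section 13, under Discontinuation of a Subject, handles dropout and removal in one sentence. When a subject drops out or "is discontinued due to protocol violations, all attempts will be made to exit the patient in accordance with the protocol requirements". The term protocol violation is not defined. Sections 6.6 to 6.8 and the Schedule of Activities contain no exit or early-termination visit.

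Section 6.7 opens its Month 3 list with "All randomized subjects will undergo the following assessments", but does not say whether this still applies after discontinuation. It dates the visit differently by arm: "Group 1: 3 months after PAP initiation" and "Group 2: 3 months after randomization".

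Section 5.1 randomises 2:1 to "expedited PAP therapy (Group 1, n~93), or standard care PAP therapy (Group 2, n~47" (approximate numbers). The synopsis describes Group 2 as "standard care PAP therapy which will commence following completion of month 3 testing". Section 5.2 states: "The subject, PI, co-investigators, coordinators, and statistician will not be blinded". Sections 6.6 and 6.7 list the PAP compliance review for Group 1 only.

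For Aim 2, Section 9.2 regresses the 3-month score on group, controlling for the baseline score. It names no analysis set and no method for missing scores.

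**The concern.** A subject who leaves before Month 3 has no outcome and drops out of the Aim 2 regression. If such exits follow from what the subject did after randomisation, the groups compared at Month 3 are no longer the groups that were randomised.

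The two arms ask for opposite behaviour. Failing to use PAP departs from assignment only in Group 1, and starting PAP before Month 3 departs from it only in Group 2. Section 13 does not say who decides on discontinuation, but the investigators and coordinators who would ordinarily do so know the allocation. Blinding the raters protects the scoring of those tested. It does not protect the choice of who is tested.

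The Month 3 anchor adds a second route to the same loss that does not need Section 13. A Group 1 subject who never starts PAP never reaches a date three months after initiation, so the schedule gives no day for the test.

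**Working it through.** **1. The plan's own power.** Section 9.1 gives SD 9, two-sided 0.05 and a 5-point SDMT difference. Section 5.1 gives 93 and 47 subjects.

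- Standard error = 9 × √(1/93 + 1/47) = 1.61, and 5/1.61 = 3.10.
- Power is 87.4% by the normal approximation and 86.9% by the noncentral t, against 86.3% stated.
- After 10 dropouts per group (83 and 37), power is 80.2% and 79.6%, against 81.2% stated. An 80/40 split gives 81.2% by the t.

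These agree closely enough, and no stated figure is disputed.

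**2. Shift from exits in Group 1 alone.** Let p be the share of the arm exited. Let d be how far the exited would have scored below the retained at Month 3, after baseline adjustment. Then mean(retained) − mean(all) = p × d. The documents give neither input, so both are assumed: p = 10-20% (about 9-19 of 93) and d = 2-5 points.

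| p | d = 2 | d = 5 |
|---|---|---|
| 10% | 0.2 | 0.5 |
| 20% | 0.4 | 1.0 |

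This is 4-20% of the 5-point target (0.2/5 to 1.0/5).

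**3. Selective exits in both arms, with no true effect.** Suppose the Group 1 subjects removed would have scored g points below those kept, and the Group 2 subjects removed g points above. Then bias = (removed₁/93) × g + (removed₂/47) × g. The rejection rate is for a two-sample t test with SD 9.

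| Removed, Group 1 / Group 2 | g | Bias (points) | Two-sided type I error |
|---|---|---|---|
| 10 / 5 | 2 | 0.43 | 5.7% |
| 10 / 5 | 5 | 1.07 | 9.5% |
| 10 / 10 | 2 | 0.64 | 6.5% |
| 10 / 10 | 5 | 1.60 | 14.5% |

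Ten per group is the dropout count in Section 9.1. The plan does not say that those losses would be selective or would come from violations.

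**4. Price of keeping everyone.** Assume that all 140 are tested, non-users gain nothing and early starters gain the full 5 points. The effect is then 5 × (1 − non-use share − early-start share).

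| Non-use, Group 1 | Early start, Group 2 | Effect | Power (t) |
|---|---|---|---|
| 10% | 0 | 4.5 | 79% |
| 20% | 0 | 4.0 | 69% |
| 30% | 0 | 3.5 | 58% |
| 20% | 10% | 3.5 | 58% |

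For the 4.0-point row the normal approximation gives 70% (4.0/1.61 = 2.48, and 2.48 − 1.96 = 0.52).

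**The case against.** The sentence in Section 13 is conditional. It describes how to handle someone who has already been discontinued and does not say that a violation must lead to discontinuation. Exiting a subject as the protocol requires could even be read as completing the Section 6.7 assessments, although nothing says so. A reader might infer that sites must exit Group 1 non-users and Group 2 early starters before the Month 3 test. The documents do not support that, because no section names either departure as a violation. For low users they point the other way. Section 9.2 models PAP use as a continuous variable, Section 9.1 powers that model on all 140, and the compliance reviews carry no minimum-use threshold.

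A reader might also infer that medication changes after randomisation are grounds for removal at the discretion of unblinded investigators. The relevant text is an eligibility criterion in Section 4.2: "Anticipated initiation, dosage change, or discontinuation in medications that could, per the opinion of the investigators, influence cognitive test scores from baseline to follow-up". It is applied before allocation, and later medication changes are only reviewed and recorded.

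Nor do exited subjects go without clinical oversight. Section 10.1 keeps those diagnosed with OSA under a sleep provider during the study and afterwards. What would stop is the study's own sleepiness and adverse-event review.

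Finally, the bias figures rest on assumed rates and gaps, and with small losses and a 2-point gap the effect is minor. All of this stands. What remains is that the term is undefined, no exit procedure exists, no text secures the Month 3 test or an analysis set, and never-starters have no test date. The continuous PAP-use model itself needs Month 3 scores from low users.

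**Conclusion.** The concern holds as a risk that the text permits. Section 13 contemplates removing randomised subjects for undefined violations, people who know the arm would probably decide, and nothing keeps those subjects in the Month 3 comparison. The missing test date for Group 1 never-starters follows directly from Section 6.7 and needs no inference about violations.

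The size cannot be fixed from the documents. With 10-20% of Group 1 exited and 2-5 points of difference left after baseline adjustment, the Group 1 mean shifts by 0.2-1.0 point, and selective loss from Group 2 would add to that. Reaching the upper end needs a residual gap as large as the whole target effect, so the lower part of the range may be the more realistic. The sponsor should correct this because the remedy is cheap and protects the randomised comparison. It is not evidence that the comparison will be biased.

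**What to change.** Amend three places.

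- **Section 13:** state that a protocol violation or a departure from assigned PAP after randomisation does not by itself end study follow-up, that Month 3 cognitive testing is sought for every randomised subject who has not withdrawn consent, and that violations are recorded by arm.
- **Section 6.7:** give Group 1 subjects who never start PAP a Month 3 test date counted from randomisation.
- **Section 9.2:** define the primary Aim 2 analysis as all randomised subjects in their assigned group, and say how Month 3 scores that are still missing will be handled.

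The safety texts need separate attention. Section 1.3 makes a high Epworth score at baseline or follow-up a cause for exclusion or discontinuation, whereas Section 13 names baseline only. The sponsor must reconcile them, and this amendment does not alter either.

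The drafting cost is a few sentences, and the Month 3 visit is already scheduled. The statistical cost is real: retained non-users dilute the effect. If 20% of Group 1 do not use PAP and gain nothing, the expected difference is about 4.0 points with 69-70% power, against the stated 86.3%. Section 9.1 should say so openly.
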